9.6.2.3 Urinalysis

Parameters include appearance, bilirubin, color, glucose, ketones, leucocyte esterase, nitrite, occult blood, pH, protein, specific gravity, and urobilinogen.

9.6.2.4 Urine Drug Screen

Parameters include: opioids, cocaine, amphetamines, methadone, cannabinoids, barbiturates, benzodiazepines, methamphetamine, and phencyclidine. All drugs detected in the urine drug screen will be listed.

9.6.3 Vital Signs

Measurements of vital signs (blood pressure systolic, blood pressure diastolic, pulse rate, oral temperature, pulse oximetry, weight, height, BMI, and waist-to-hip ratio) will be summarized using descriptive statistics at each scheduled visit and time point including change from baseline and percentage change from baseline.

Listings of all vital sign assessments will be provided in the following groups:

- Blood pressure systolic, blood pressure diastolic, pulse rate, oral temperature, and respiration rate
- Pulse Oximetry
- Body weight, BMI, and waist-to-hip ratio.

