## 6.4 Vital Signs

Evaluation of vital signs will be performed after the subject has been supine for  $\geq 3$  minutes and will include a measurement of systolic and diastolic BP, pulse rate, pulse oximetry, respiratory rate, and oral temperature.

If clinically significant findings, as determined by the Investigator or medically qualified sub-investigator, occur in any vital sign measurement, that measurement will be captured as an AE and repeated at medically appropriate intervals until the value returns to an acceptable range, a specific diagnosis is established, or the condition is otherwise explained.

Assessments will be recorded in the source documents and eCRF and will be performed at the time points detailed in the SOE ([Appendix 1](#), [Appendix 2](#), [Appendix 3](#), [Appendix 4](#), and [Appendix 5](#)).

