#### 9.5.1.2 Laboratory Data

At each visit where clinical laboratory assessments are conducted, summary statistics for the absolute laboratory value and the changes from baseline will be presented.

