AE = adverse event; ASI = Addiction Severity Index; BDI-II = Beck Depression Inventory II; BMI = body mass index; BPI = Brief Pain Inventory Short Form; COWS = Clinical Opiate Withdrawal Scale; eC-SSRS = electronic Columbia Suicide Severity Rating Scale; D = Day; ECG = electrocardiogram; EQ-5D-5L = EuroQol EQ-5D-5L; HCRU = Healthcare resource utilization; Inj. = injection; IXRS=Interactive voice/web response system; MSQ = Medication Satisfaction Questionnaire; PK = pharmacokinetic/pharmacokinetics; SF-36v2 = 36-Item Short Form Health Survey, Version 2; SC = subcutaneous; SOWS = subjective opiate withdrawal scale; TEA = Treatment Effectiveness Assessment; TLFB = Timeline Followback; VAS = Visual Analog Scale

1. Includes blood pressure, pulse oximetry, pulse rate, respiratory rate, and oral temperature which must be taken after subject is supine  $\geq 3$  minutes. On injection day 1, vital signs will be taken  $\leq 60$  minutes prior to SC injection, and then 0.5 ( $\pm 15$  minutes), and 2 hours post SC injection ( $\pm 15$  minutes). For all subsequent injection days, vital signs will be taken  $\leq 60$  minutes prior to SC injection, and 1 hour post SC injection ( $\pm 15$  minutes). For non-injection days, vital signs will be taken at approximately the same time of day as the Day 1 pre-injection vital signs.
2. On Injection day 1, an ECG will be performed  $\leq 60$  minutes prior to SC injection, and then 0.5 ( $\pm 15$  minutes), and 2 hours post SC injection ( $\pm 30$  minutes). For all subsequent injection days, an ECG will be recorded  $\leq 60$  minutes prior to SC injection, and 1 hour post SC injection ( $\pm 30$  minutes). For non-injection days, an ECG will be performed at approximately the same time of day as the Day 1 pre-injection ECG. All ECGs must be performed prior to laboratory assessments.
3. On injection days blood and urine samples will be taken  $\leq 60$  minutes prior to SC injection and after the ECG has been performed.
4. Only for female subjects who are of childbearing potential (not postmenopausal or surgically sterile for at least 1 year).
5. An additional urine drug screen can be done if use is suspected. Oxycodone may not show up in all opiate assays and should be assessed separately.

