9.6.1.9 Potentially Pertaining to Respiratory Depression and Failure

A summary of TEAEs potentially pertaining to respiratory depression and failure, as defined in [Appendix 2](#), will be summarized by SOC and PT for the Safety Analysis Set.

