9.6.2 Laboratory Data

Laboratory data will be reported using International System (SI) units as collected by the central laboratory. Unless otherwise specified, all continuous laboratory data will be summarized using descriptive statistics (n, mean, SD, median, min, and max) for each scheduled study assessment as well as change from baseline and percentage change from baseline [if applicable] by parameter class (hematology, chemistry, and urinalysis). The following parameters will have graphs of the mean values by visit through the end of study: hematocrit, alkaline phosphatase (ALP), alanine aminotransferase (ALT), amylase, lipase, trypsinogen, aspartate aminotransferase (AST), creatinine clearance, creatinine kinase, gamma-glutamyl transferase, and bilirubin (from serum chemistry results). All laboratory assessments include a baseline summary as defined in [Section 5](#) unless otherwise indicated. Hematology, chemistry, and urinalysis data will be summarized by displaying shifts from baseline value (low/normal/high) to last assessment on treatment and worst result on treatment (for only subjects with normal as baseline) considering both scheduled and unscheduled assessments. All laboratory assessments will be listed by panel with the corresponding normal ranges for each parameter. Screening laboratory will be provided in a separate listing.

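### SAP 9.6.3 omits respiratory rate from the vital signs to be summarised, so a protocol-defined vital sign in a depot-opioid safety study is only listed; the SAP should also say how the hormone panel is reported.

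*SAP*

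**What the plan says.** **Respiratory rate.** Protocol 6.4 states that vital signs "will include a measurement of systolic and diastolic BP, pulse rate, pulse oximetry, respiratory rate, and oral temperature". The footnotes to the schedules of events (Protocol Appendices 2 to 5) repeat this and set the timing. On Day 1 there is a reading before the injection and two after it; for later injections Appendix 2 begins "For all subsequent injection days, vital signs will be taken" and goes on to require one before and one after. Non-injection clinic visits have one.

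The Safety Analyses part of the Protocol Synopsis counts vital signs among the safety variables and commits to descriptive statistics for continuous ones. SAP 4.1 makes vital sign measurements a primary variable.

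SAP 9.6.3 then names what is summarised by visit and time point, with change and percentage change from baseline: "blood pressure systolic, blood pressure diastolic, pulse rate, oral temperature, pulse oximetry, weight, height, BMI, and waist-to-hip ratio". Its first listing group reads "Blood pressure systolic, blood pressure diastolic, pulse rate, oral temperature, and respiration rate".

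**Hormone panel.** Protocol 6.6.1, Table 2, includes a panel of ACTH, FSH and total and free testosterone. Protocol 9.5.1.2 says: "At each visit where clinical laboratory assessments are conducted, summary statistics for the absolute laboratory value and the changes from baseline will be presented". SAP 9.6.2 presents laboratory summaries "by parameter class (hematology, chemistry, and urinalysis"), and the parameter lists in 9.6.2.1 to 9.6.2.4 contain no hormone.

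**The concern.** The primary objective is long-term safety of a monthly opioid depot, and respiratory depression is one of the SAP's own special-interest topics: section 9.6.1.9 plans "A summary of TEAEs potentially pertaining to respiratory depression and failure". Respiratory rate is a repeatedly measured quantity bearing directly on that topic. If the SAP is programmed as written, the report will contain no mean, spread or change from baseline for it, at any visit or post-injection time point. A modest fall across the population that no investigator thought clinically significant in any one subject would appear neither in a vital-sign table nor in the adverse events. It could be found only by working through individual listings.

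Neither a reason nor a declaration is given. Protocol 9.1 says departures from its planned analyses will be recorded in the SAP. SAP 1.1 records six, and this is not one of them.

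**Working it through.** No sample size or error rate is involved. The check compares the protocol with the SAP and counts scheduled collections.

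**1. Vital signs, measure by measure.**

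| Measure in Protocol 6.4 | Summarised in SAP 9.6.3 | Listed in SAP 9.6.3 |
|---|---|---|
| Systolic BP | yes | yes |
| Diastolic BP | yes | yes |
| Pulse rate | yes | yes |
| Pulse oximetry | yes | yes |
| Oral temperature | yes | yes |
| Respiratory rate | **no** | yes |

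Five of the six protocol vital signs are summarised. The other four entries in the SAP's list of nine are body measurements (5 + 4 = 9). Because respiratory rate is in the listing group of the same section, the SAP's authors knew it was collected. Its absence from the summary list looks like a drafting slip.

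**2. Scheduled respiratory-rate readings from Day 1 onward.** Inputs: the vital-signs rows and footnote 1 of Appendices 2 to 5. Readings = Day 1 readings + 2 × later injections + non-injection visits.

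- De novo: Day 1 has 3; there are 11 later injections; the non-injection visits are Days 2, 8, 15, 22, 43, 71, 99, 127 and 337, which is 9. Total 3 + 2 × 11 + 9 = 34.
- Roll-over: Day 1 has 3; there are 5 later injections; the non-injection visits are Days 2, 8, 15, 22, 43, 71, 99, 127 and 169, which is 9. Total 3 + 2 × 5 + 9 = 22.

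The Day 1 pre-injection reading would normally serve as the SAP 5.0 baseline. That leaves 34 − 1 = 33 and 22 − 1 = 21 post-baseline readings.

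**3. Hormone panels from Day 1 onward** (hormone-panel rows of Appendices 2 to 5).

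- De novo: Days 1, 85, 141, 169, 253, 309 and 337 = 7.
- Roll-over: Days 1, 85, 141 and 169 = 4.

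Both groups also have a screening panel; for roll-over subjects it comes from the end-of-study visit of the preceding trial.

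**4. Is the hormone panel meant to be summarised?**

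- For: Table 2 lists it among the laboratory tests, and Protocol 9.5.1.2 exempts no panel. The opening of SAP 9.6.2 refers to continuous laboratory data in general.
- Against: Protocol 9.5.1 and the Synopsis describe the laboratory safety variable by three classes only (haematology, chemistry, urinalysis), and 9.5.1.2 is a subsection of 9.5.1. The opening sentence of SAP 9.6.2 ends by naming the same three.

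The texts do not settle it.

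**The case against.** The SAP is not silent on respiratory safety. Pulse oximetry is summarised at every scheduled visit and time point with change from baseline. The respiratory table in SAP 9.6.1.9 uses a term list (SAP Appendix 2) that includes Respiratory rate decreased, Bradypnoea and Hypoventilation. Protocol 6.4 requires a clinically significant vital-sign finding to be recorded as an adverse event. Every respiratory-rate value will be listed. All of this stands, and it means a reader should not infer that respiratory depression goes unexamined. What remains uncovered is change below the investigator's threshold of clinical significance, which is what a summary table is for.

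The table shells are in a separate document (SAP Appendix 3) that was not available for this review and may include respiratory rate. SAP 9.0 also has a general rule for summarising continuous variables, and Protocol 9.5.1.3 does not itself prescribe a table. These points soften the concern but do not remove it: a section that names its measures explicitly will be read as complete, and if the shells do include the table, the text should agree with them.

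A reader might also infer that leaving the hormone panel out of SAP 9.6.2 is a second undeclared departure from the protocol. The documents do not support that. On the narrower reading of Protocol 9.5.1 there is nothing to declare, and even the panel's place in the listings has to be inferred from a generic sentence about listing by panel.

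Nor do the documents call for a pre- to post-injection contrast or shift table for respiratory rate, since the SAP sets neither for any vital sign. The same holds for hormone shift tables and for testosterone by sex. They might be useful, but their absence is not a defect against this plan.

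**Conclusion.** The respiratory-rate point holds. One of six protocol-defined vital signs, with about 34 scheduled readings per completing de novo subject and 22 per roll-over subject, is listed but not summarised, and SAP 1.1 does not say so. The consequence is a reporting gap in the primary safety analysis. No data are lost, and oximetry and adverse-event tabulation partly cover the topic. The effect on any conclusion cannot be sized from the documents; the counts describe only how much collected information goes unsummarised. They assume full attendance and exclude unscheduled and Run-In readings.

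The hormone point is secondary and is a request for clarity: a panel collected 7 times (de novo) or 4 times (roll-over) from Day 1 is never named in the SAP text available, and the protocol can be read either way.

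Both conclusions rest on the SAP text without its table shells.

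**What to change.** **Respiratory rate.** Add it to the summary list in SAP 9.6.3, with descriptive statistics and change from baseline at each scheduled visit and time point, exactly as for the other vital signs. Check that the shells agree. The cost is one entry in the text and one more parameter in an existing table.

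**Hormone panel.** Choose one and write it down: either add it to SAP 9.6.2 as a summarised class, with values and change from baseline at its scheduled visits, or state that it is listed only. The first needs one further laboratory table; the second needs one sentence. Neither change needs new data.

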9.6.4 Other Safety Variables

9.6.4.1 12-lead Electrocardiograms

Results from 12-lead ECGs as determined by central reader will be categorized as normal or abnormal and will be summarized using shift from baseline to end of study/early termination using frequency counts. An additional table summarizing shift from baseline to worst result on study will be presented. ECG interval measurements including change from baseline will be summarized by time point using descriptive statistics for actual value and change from baseline. Parameters will include heart rate (beats/min), PR Interval (msec), QRS Duration (msec), RR interval (msec), QT interval (msec), adjudicated QTc-Bazett (msec), and adjudicated QTc-Fridericia (msec). Additionally, the number and percentage of subjects with a >30 msec or >60 msec change from baseline will be summarized by visit and at any point throughout the study. ECG results will be listed for interpretation and for the interval measurements.

9.6.4.2 Suicidality

Suicidal ideation and suicidal behavior responses (Yes/No) will be summarized using counts and percentages in the Safety Analysis Set. Shift tables to demonstrate changes in eC-SSRS categories and changes in suicidal ideation and behavior scores, as defined in [Section 5](#) from baseline during the open-label treatment period will be presented. eC-SSRS and suicidal ideation responses will be listed separately. The suicidal ideation intensity ratings, each of the five items and the total score of the intensity for subjects with an ideation will be listed.

Several subjects completed the baseline-lifetime version of the e-CSSRS questionnaire that was intended to be used at Screening rather than the 'since last visit' version **required** at all subsequent visits. The data collected using the wrong version will be presented in the listings, but will not be presented in the summary tables.

9.6.4.3 Local Injection Site Tolerability

Local injection site tolerability as assessed by the Injection Site Grading scale will be summarized by category (pain, tenderness, erythema/redness, induration, and swelling) and severity at each time point and at any time using frequency counts and percentages.

Sponsor: Indivior Inc.
Protocol no: RB-US-13-0003

A separate listing will be presented for severe/life threatening responses with their corresponding VAS scores.

The injection site tolerability results will be listed.

9.6.4.4 Injection Site Pain

Injection Site Pain VAS scores will be summarized by subject type, injection, and time point after injection. The burning/stinging categorical variable (Yes/No) will be summarized by percentage of responses in each subject type at each time point. Attempted removal results will be summarized by percentage of subjects with attempted removal in each subject type at each visit.

Separate listings for burning/stinging and attempted removal evaluations will be provided. A listing of injection site pain VAS scores will also be provided.

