Test Product, Dose, and Mode of Administration: 300 mg buprenorphine in RBP-6000, subcutaneous injection 100 mg buprenorphine in RBP-6000, subcutaneous injection
Duration of Study Treatment: This will be a multiple-dose study, with the first investigational product administration (RBP-6000 containing 300 mg buprenorphine) on Day 1. The expected maximum duration of participation for de novo subjects is up to approximately 55 weeks, consisting of up to 7 days of screening, up to 14 days SUBOXONE sublingual film Run-In, up to a 48-week open-label treatment period, and a 4-week safety follow-up telephone call. The expected maximum duration of participation for roll-over subjects is up to approximately 31 weeks, consisting of up to a 7-day screening period, up to 14 days SUBOXONE sublingual film Run-In, a 24-week open-label treatment period, and a 4-week safety follow-up telephone call. Subjects who enroll in the INDV-6000-301 study are not required to complete the safety follow-up telephone call.
Safety Assessments: Safety objectives for this study are to evaluate the safety and tolerability of RBP-6000 (100 mg and 300 mg) SC injection treatment in subjects with opioid use disorder. Safety assessments will include the following: frequency of all AEs, serious AEs (SAEs), discontinuations from study due to AEs; local injection site tolerability (e.g., injection site grading); injection site pain using a subject-reported VAS; suicidality using the eC-SSRS, use of concomitant medications; changes in clinical laboratory results; vital sign measurements; 12-lead ECGs, which will be interpreted by a central facility; physical examination results; body weight, height, and body mass index (BMI), and abdominal fat measurement (waist-to-hip ratio).
Clinical Outcome Assessments: Clinical outcome assessments will include the UDS for opioids and other drugs; self-reported use of illicit opioids, other drugs, and alcohol on the TLFB; COWS, SOWS, and Opioid Craving VAS.

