### 1.4.1 Summary of Nonclinical Data

Nonclinical data suggest that toxicity from RBP-6000 is unlikely at the doses planned for this clinical study. The no observable adverse effect levels (NOAELs) were determined to be 250 mg/kg (rat) and 40 mg/kg (dog) following single SC injections of RBP-6000 in 4-week toxicity studies. These levels are equivalent to human buprenorphine doses of 2419 mg and 1333 mg, respectively (based on 60 kg body weight and calculated according US Food and Drug Administration guidance [FDA 2005]). These levels provide approximately 8.1x (rat) and 4.4x (dog) safety margins when compared to the 300-mg buprenorphine dose in humans (based on 60 kg body weight and calculated according US Food and Drug Administration guidance [FDA 2005]). Systemic effects seen in the rat and dog 4-week toxicity studies were related to the pharmacology of buprenorphine or local tolerance effects of the formulation as a result of high dose and volume, so the safety margins are considered acceptable.

Chronic repeated-dose studies were conducted in rats and dogs dosed with RBP-6000 once every 4 weeks for 6 or 9 months, respectively. These studies demonstrated systemic effects consistent with buprenorphine administration, such as stained fur, aggressive behavior, decreased activity,

reduced food consumption and body weight gain, and abnormal feces. Minimal to mild lung alveolar macrophage infiltration and pancreatic acinar cell apoptosis were seen with increased incidence in rats, but not dogs, treated with RBP-6000. Injection site findings were seen in both species, characterized microscopically by minimal to moderate granuloma formation. Injection volumes were high, being 2.73 mL/m^2 in rats and 3.64 mL/ m^2 in dogs, compared with a volume of 0.62 mL/ m^2 at the highest proposed clinical dose, contributing to these local findings. Systemic chronic NOAELs were considered to be 10 mg/kg in rats and 40 mg/kg in dogs.

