## 9 PLANNED STATISTICAL METHODS

### 9.1 General Considerations

A Statistical Analysis Plan (SAP) will be prepared after the protocol is approved and before database lock occurs. The SAP will provide further details regarding the definition of analysis endpoints, data handling rules, and the statistical methodology to be used to address all study objectives. The SAP will also include formats for the summary and analysis tables, listings, and graphical displays.

This section describes methods for sample size determination, analysis populations, and planned analyses for, safety, PK, and clinical outcomes endpoints. Additional unplanned analyses may be required after all planned analyses have been completed. Any unplanned analyses will be clearly identified in the clinical study report. Any deviations from the analyses described below will be included in the SAP, which will form Appendix 16.1.9 of the clinical study report.

Continuous variables will be summarized using descriptive statistics such as means, standard deviations (SD), medians, minimums, and maximums. Categorical variables will be reported as frequency counts (including number missing) and the percentage of subjects in corresponding categories. Individual subject data will be presented by subject in data listings. Data listings will include all data collected from the initial screening visit to the end of study for all subjects enrolled.

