#### 9.5.1.4 Other Variables Related to Safety

Results from 12-lead ECGs will be categorized as normal, abnormal clinically significant, or abnormal not clinically significant and will be summarized by time point using frequency counts

and percentages. ECG interval measurements as well as change from baseline will also be summarized by time point using descriptive statistics (mean, median, SD, minimum, maximum). Additional analysis of ECG parameters will be outlined in the SAP.

Medical history will be coded using MedDRA and summarized by treatment group as described for AEs (Section 9.5.1.1). Body weight, height, BMI, and abdominal fat measurement (waist-to-hip ratio) will be summarized using descriptive statistics (mean, median, SD, minimum, maximum), including change from baseline.

Total eC-SSRS scores will be summarized using descriptive statistics (mean, median, SD, minimum, maximum), including change from baseline. Subjects' self-reported illicit drug use from the TLFB will be summarized as descriptive statistics.

Prior and concomitant medications will be coded using the most recent version of the World Health Organization (WHO) Drug dictionary. Incidence (number and percent of subjects reporting the medication at least once during the study) will be summarized for all concomitant medications.

Local injection site tolerability as assessed by the Injection Site Grading scale will be summarized by category and severity using frequency counts and percentages similar to summaries for AEs (Section 9.5.1.1). Injection Site Pain VAS scores will be summarized by dose, injection, and time point after injection. The burning/stinging categorical variable (Yes/No) will be summarized by percent of responses in each treatment.

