1.1 Changes from Protocol

The following changes to the analysis planned in the protocol were made:

- The addition of an analysis set (Run-In Safety Analysis Set) was made to aid in the analysis of the Run-In period.
- Electrocardiograms (ECGs) overall impression summaries will only be summarized by normal or abnormal; protocol says they should be summarized by normal, abnormal not clinically significant, or abnormal clinically significant, but there is no distinction of clinical significance for abnormal results.
- There will be no mixed-effect model for repeated measure analysis on the clinical outcome data, Clinical Opiate Withdrawal Scale (COWS), Subjective Opiate Withdrawal Scale (SOWS), and Opioid Craving Visual Analog Scale (VAS), due to the nature of the study design.
- The Clinical Outcome Assessment Analysis Set has been removed since this is a safety study.
- Total score for electronic Columbia Suicide Severity Rating Scale will not be summarized.
- Physical examination data is collected as a part of the corresponding safety assessment (i.e. adverse events (AEs), vital signs).

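### The SAP summarises injection-site pain VAS by subject type where the protocol planned it by dose, without declaring the change; separately, its exposure categories stop below 52 weeks although permitted spacing runs past that

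*SAP*

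**What the plan says.** **Pain VAS.** Protocol 9.5.1.4: "Injection Site Pain VAS scores will be summarized by dose, injection, and time point after injection". SAP 9.6.4.4: "Injection Site Pain VAS scores will be summarized by subject type, injection, and time point after injection". The two sentences differ in one factor.

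**Burning/stinging.** Protocol 9.5.1.4: "The burning/stinging categorical variable (Yes/No) will be summarized by percent of responses in each treatment". SAP 9.6.4.4 has it "summarized by percentage of responses in each subject type at each time point".

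**Declaring changes.** Protocol 9.1: "Any deviations from the analyses described below will be included in the SAP". SAP 1.1 opens with "The following changes to the analysis planned in the protocol were made" and lists six items: the Run-In analysis set, ECG categories, dropping the repeated-measures model, removing the clinical outcome set, the eC-SSRS total, and physical examination data. None concerns injection-site pain, burning/stinging or dose.

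**Why dose matters here.** The protocol synopsis (Safety Assessments) reads: "Safety objectives for this study are to evaluate the safety and tolerability of RBP-6000 (100 mg and 300 mg) SC injection treatment". SAP 3.0 gives every subject 300 mg on Day 1 and lets the investigator move later doses between 100 mg and 300 mg, in both subject types.

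**Exposure.** SAP 9.4 counts from the first injection in this study to 28 days after the last, in categories from 0-<4 up to 48-<52 weeks. Protocol 5.3 allows 26 to 32 days between injections. SAP 3.1 sizes the study so that at least 100 subjects reach one year of treatment.

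**The concern.** The primary objective is long-term safety and tolerability, and the safety objective names both doses. The protocol planned one table in which a reader could set injection-site pain at 100 mg beside pain at 300 mg. The SAP text removes it and does not say so. Anyone who relies on SAP 1.1 to see how the analysis departs from the protocol would not learn that the dose display has gone.

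The exposure table is a smaller matter of the same kind. The study size rests on a one-year count, yet the listed categories have no level at or above 52 weeks, and some schedules that follow the protocol would fit none of them.

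**Working it through.** **1. Can subject type stand in for dose?** No. Both types start at 300 mg and both may receive either dose afterwards. SAP 9.6.4.4 does hold subject type, injection number and time point fixed, so those factors are not confounded with dose within a cell. What happens is pooling: from injection 2 onward a cell may contain both doses. At injection 1 every dose is 300 mg, so nothing is lost there.

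**2. Effect of pooling.** Let f be the share of injections in a cell given at 100 mg and d the mean difference in VAS between doses. The cell mean then differs from the 300 mg mean by f × d. The documents give neither f nor d, so both are assumptions. With d = 10 mm:

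- f = 0 (injection 1): 0 mm
- f = 5%: 0.05 × 10 = 0.5 mm
- f = 50%: 0.50 × 10 = 5.0 mm

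The table shows only the pooled mean, so d cannot be recovered from it. The dose of each injection (SAP 9.4) and the VAS scores (SAP 9.6.4.4) are both promised as listings. The data exist, but no summary joins them.

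**3. Exposure.** The planned figures reproduce: 12 × 28/7 = 48 weeks and 6 × 28/7 = 24 weeks; participation is 1 + 2 + 48 + 4 = 55 weeks and 1 + 2 + 24 + 4 = 31 weeks.

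By the duration formula in SAP 5.0, days = (n − 1) × spacing + 28 + 1:

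| Injections | Spacing (days) | Days | Weeks |
|---|---|---|---|
| 12 | 26 | 11 × 26 + 29 = 315 | 45.0 |
| 12 | 28 | 11 × 28 + 29 = 337 | 48.1 |
| 12 | 32 | 11 × 32 + 29 = 381 | 54.4 |
| 6 | 28 | 5 × 28 + 29 = 169 | 24.1 |
| 6 | 32 | 5 × 32 + 29 = 189 | 27.0 |

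A de novo subject reaches 52 weeks (364 days) at a mean interval of (364 − 29)/11 = 30.5 days, which is inside the permitted range. Four one-week delays under protocol 6.8 on an otherwise nominal schedule do the same: (337 + 28)/7 = 52.1 weeks. These subjects lie beyond the last category.

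**4. Adverse-event window (bears only on the optional item).** Subject incidence is shown over up to 48 planned weeks for de novo and 24 for roll-over subjects. Assume equal weekly risk in both groups, a 10% risk in weeks 1-24 and full retention, so roll-over shows 10.0%. De novo then shows:

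- constant hazard: 1 − 0.9² = 19.0%
- hazard halved after week 24: 1 − 0.9 × √0.9 = 14.6%
- all events early: 10.0%

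The gap runs from none to nearly double, depending on when events occur.

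**The case against.** **The study is descriptive and the investigator chooses the dose, so a dose table is not a randomised comparison.** True, and the table should be labelled accordingly. The protocol planned it in the same open-label design, so this does not explain removing it without a declaration.

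**Burning/stinging may not be a departure.** This stands. The protocol's wording refers to treatment, not dose. For demographics (protocol 9.4) and medical history (protocol 9.5.1.4) it uses treatment group, which SAP 9.3 and 9.3.1 render as subject type. The synopsis lists 300 mg and 100 mg as the products, which points the other way. A reader might infer that a by-dose analysis was dropped here too; the text is ambiguous and only supports asking for clarification.

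**The nonclinical text shows a dose effect.** A reader might infer this from "local tolerance effects of the formulation as a result of high dose and volume" in protocol 1.4.1. That sentence concerns rat and dog studies with no-effect levels put at about 8.1 and 4.4 times the 300 mg human dose. It does not show a 100 mg v 300 mg difference in people.

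**The adverse-event tables conform to the protocol.** They do. Protocol 9.5.1.1 asks for subject incidence during the study, no between-group test is planned, and SAP 9.4 summarises exposure. A reader might call the missing common window an error; no document promises one.

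**The nominal course fits the exposure table.** At 48.1 weeks it does, and per-subject doses and intervals are listed. If one year meant 12 injections, the top category would show nominal completers, but the documents do not define it so. The gap affects only longer schedules.

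**Conclusion.** The pain VAS point holds on the wording of the two documents: dose was replaced by subject type, SAP 1.1 does not say so, and no pain summary in the SAP text separates the two doses named in the safety objective. How much is hidden depends on the dose mix and the true difference. The 0.5 to 5.0 mm range rests on an assumed 10 mm difference and is illustrative only.

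The exposure point also holds, on a narrower footing: the categories do not cover the permitted range, which extends to 54.4 weeks, and the table cannot show 52 weeks or more.

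Two further inferences are not supported. One is that the SAP must tabulate exposure across RB-US-13-0001 and this study because SAP 3.3 counts the one-year target over both. The other is that roll-over subjects must be split by their RB-US-13-0001 assignment. SAP 1.0 confines the plan to this study's data, SAP 8.1 lists no source for the other study's assignments or dosing dates, and no document requires either table.

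All of this rests on the SAP text. The table shells named in SAP Appendix 3 were not available and may contain additional displays; even so, SAP 9.6.4.4 and 1.1 would need to agree with them.

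**What to change.** 1. In SAP 9.6.4.4, add pain VAS by dose of that injection (100 mg / 300 mg), injection number and time point. Show burning/stinging by dose in the same way and state what the protocol's reference to treatment means. Label both as descriptive because the investigator selects the dose. The subject-type tables can stay. Record any remaining departure from protocol 9.5.1.4 in SAP 1.1.
2. In SAP 9.4, add an exposure category of 52 weeks or more.

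Optional, as an addition to a summary that already follows the protocol: treatment-emergent adverse events with onset in weeks 1-24 for both subject types, with de novo onset after week 24 shown separately. This puts the columns on a common window. It does not remove differences due to roll-over subjects being selected completers or, for some, already exposed to RBP-6000.

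The cost is two descriptive tables, one extra category and a line in SAP 1.1, all from data already collected in this study. The optional item adds one more table.
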